6.0 Incomplete Disclosure or Deception: N/A

7.0 Recruitment:

Study Participants: During phase 1, we will recruit 108 study participants from each of the participating HV programs. We will enroll 108 HV clients at 10-12 HV programs, 54 women will receive Mothers and Babies 1-on-1 without text message enhancements and 54 women will receive Mothers and Babies 1-on-1 with text message enhancements. Of the 108 women, 16 will be recruited for focus groups phase 2 of the study.

During phase 2 of the study we will conduct focus groups with the identified 16 women from the 108 group that participated in phase 1 of the study. We will also include their male partners (n=16) in two focus groups of 8 participants. Additionally we will recruit 36 women and their male partners to participate in the FAB Pilot Study.

Home Visitors: We will recruit approximately 36 home visitors from 10-12 participating HV programs throughout the state of Illinois. All HV programs recruit women at high risk for poor pregnancy and/or parenting outcomes via referrals from prenatal care clinics, community outreach, and current program participation. All of the home-visitors who are being recruited through the participating home-visiting sites have been previous trained and are currently implementing Mothers and Babies 1-on-1. Home visitors that have not been trained will receive an in-person training (see training section for more detail). Each home-visitor will identify 1-4 client that will participate in study activities, of these clients 1-2 will receive MB without Text and 1-2 will receive MB with Text. All home-visitors will implement MB without text and MB with text. Programs will initially implement MB 1-on-1 and will recruit MB participants for six months before crossing over to recruit MB-TXT participants for 6 months. To pilot FAB 1-3 home-visitors from each program will identify 1-4 client dyads that will participate in FAB pilot study activities; Home-visitors who will implement FAB will recruit dyads.

We anticipate 16 home-visitors will participate in focus groups during phase 1 and 2 of the study. 10-12 HV programs will be recruited to implement the FAB pilot.

Recruitment Procedures/Attrition: Recruitment procedures will be identical to those used in a previous RCT of MB in HV programs conducted by [name]. A postcard and/or flyer will be provided to the participating HV sites and the potential eligible study participants prior to NU research staff calling the study participants. The postcard/flyer will explain the purpose and overview of the study. Prior to beginning program implementation, potential study participants contact information will be obtained by the participating trained HV sites. The HV programs will fill out the referral form for eligible and interested participants, the form will be faxed or e-mailed to the Project Manager. The Project Manager and Research Assistant will share responsibility for calling each woman receiving HV services to tell them more about the recruitment and consenting process. A recruitment letter will be sent to the participants by the RA asking them to participate in the research study if the research team is unable to reach them by phone or email. The NU research team will also email the survey link to the study participants using email addresses provided by the HV sites, the link on NU REDCap database to be able to consent to participate in the program and complete a baseline assessment. The surveys will be available in both English and Spanish.

We will obtain names, phone numbers, and addresses of women and their partners. Individuals who meet our criteria for study eligibility but who are not interested in participating in our research activities will still be able to participate in the MB intervention. Based on previous research, we expect that fewer than 5% of eligible participants will opt out of research activities.

Phase 1 (MB-TXT RCT)

Each program will send contact information for an eligible participant to the Project Manager. The Research Assistant or Project Manager will contact these women to introduce women to the study, answer questions about participation, and ascertain interest in study participation. For women expressing interest, the Research Assistant will send an email link to the REDCap data collection portal to conduct the baseline assessment. Before completing the assessment, participants will provide informed consent via the REDCap system. Informed consent and surveys will be conducted by telephone with participants who do not have consistent internet access. These recruitment procedures have been used successfully in [name] current HV research in Illinois.

Phase 2 (FAB Development and Pilot)*Focus Groups*

Informed consent forms will indicate that women participating in the MB-TXT intervention may be approached to participate in a focus group upon completion of the intervention. We anticipate recruiting women from the HV programs participating in MB-TXT. Should we have difficulty recruiting study participants from these programs, we will recruit from programs that have been previously trained in MB 1-on-1. .

To recruit male partners for the focus groups, we will use recruitment procedures used by Co-I [name] in his previous research. We will first check with the female client that she agrees that her male partner should be invited to participate; this is an important consideration given the multitude of reasons female partners may not want their partner to engage in this project (e.g., domestic violence). If the female client agrees and provides contact information for their partners, we will directly contact fathers to inform them about the focus groups and gauge their interest in participating. This may either occur through attempts at in-person or phone exchanges between the Project Manager/Research Assistant and fathers.

HV programs participating in this project understand that one goal is to develop intervention materials for fathers of HV clients, and are aware that home visitors from programs implementing MB-TXT will be recruited for focus group participation. Recruitment of home visitors for focus groups will be done by the Project Manager. We anticipate that home visitor focus groups will be conducted during a regularly scheduled supervision meeting among HV staff—a recruitment method that has proven effective in previous studies conducted by [name].

FAB Pilot

We anticipate recruiting women from the HV programs participating in MB-TXT and 2-3 new programs. We will take a three-pronged approach to recruitment and engagement of fathers in the pilot of FAB intervention. First, rather than take a maternal-gatekeeping approach to recruitment, we will take a father-centric approach where we directly contact fathers to inform them about this study. The home visitor will explain the pilot to her client and her partner during a regularly scheduled visit. The home visitor will leave brochures for both the mothers and fathers. Father-specific recruitment materials left for fathers who are not present at the time of recruitment by the HV staff. Second, all study materials will include father-specific language, images, and content supporting their role and importance to the family and the study. If the dyad is interested the HV will fill out the referral form and fax or e-mail it to the Project Manager. The Research Assistant or Project Manager will contact the female client and her partner separately and explain the study. For the uncontrolled pilot, recruitment procedures for females will be similar to those described earlier for Phase 1 (MB TEXT RCT). Recruitment procedures for male partners will use the same strategies as listed above. Male partners will also be sent an email link to the REDCap data collection portal to conduct baseline assessments and will be asked to provide informed consent via REDCap prior to completing this assessment. Informed consent and surveys will be conducted by telephone with participants who do not have consistent internet access. These recruitment procedures have been used successfully in [name] current HV research in Illinois.

Informed consent forms will indicate that male partners participating in the FAB intervention may be approached to participate in a focus group or key informant upon completion of the intervention.

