We will conduct a cluster RCT to determine the feasibility and acceptability of the MB-TXT intervention and calculate a preliminary effect size to determine a sample size for a future RCT. This RCT will also allow us to examine MB-TXT effects on proposed mechanisms underlying intervention efficacy. Cluster allocation by HV program minimizes contamination between study groups. We will work with 10-12 HV programs that have been trained on MB 1-on-1 and have working relationships with the PI. These programs provide a geographically, racially, and ethnically diverse set of recruitment sites. These programs are part of a network of Illinois HV programs overseen by the Illinois Governor's Office of Early Childhood Development which has supported scaling MB throughout Illinois and is enthusiastic about using text messaging to enhance intervention effectiveness. We will use a stepped wedge design—a form of RCT that involves sequential, but random, rollout of the intervention over multiple time periods. We have created two HV program clusters. Both clusters will initially implement MB 1-on-1 and will recruit MB participants for one quarter (i.e., three months) before crossing over to recruit MB-TXT participants for one quarter. MB-TXT's core curriculum is identical to MB 1-on-1 and adds a series of text messages throughout the curriculum.

Study Conditions:

MB 1-on-1. Half of our study participants (n=54) will receive MB 1-on-1. MB 1-on-1 is a manualized 12-session intervention divided into five modules. An introductory 2-session module establishes key

PROTOCOL TITLE: The Mothers and Babies Text Project

concepts related to stress, monitoring of one's mood, and ways in which one's mood influences one's internal thoughts and external environment; three 3-session modules correspond with key cognitive-behavioral elements: pleasant activities, thoughts, and social support/contact with others; a 1-session summary reviews content and identifies areas for future use of MB skills. Throughout MB, mood management skills are integrated using psycho-educational activities that encourage participants to understand connections between their mood and their activities, thoughts, and contacts with others. Content is tailored to specific needs and issues of pregnancy and the postpartum periods. Each MB session lasts 15-20 minutes and is delivered as part of a regularly scheduled home visit.

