
Phase 1 Focus Groups

We will also recruit and conduct two focus groups with 16 HV supervisors/managers and home visitors beginning in phase one and into phase 2 of the study.

Training and Supervision of HV programs. The majority of participating All HV programs have been trained on MB 1-on-1 and are currently implementing the curriculum. Programs new to the MB Course will receive in-person training from the PI and/or study team. All programs will receive a half-day refresher training on MB along with guidelines on implementing MB-TXT conducted by Co-I [name] and PI [name]. All programs will receive supervision from PI [name] after the first implementation of the intervention begins at the HV programs

Participant Screening: Participants will initially be screened for eligibility criteria by their home visiting program sites. Upon permission from the potential study participant, program sites will fill out a referral form, which will include the potential study participants name and contact information, and send it to the research team. The HV will explain the study and provide a brochure with study details during the referral process. Once the program sites refer potential study participants, a member of the study team will call the participant using the "Phone Script for Referrals" to screen the potential study

participant for eligibility criteria and move forward with the consent process either via telephone or a REDCap survey link.

Participant Outcomes Surveys:

Clients MB TEXT: Participant outcomes will be collected at three time points—baseline and 6 months post-intervention. Participants will receive \$20 remuneration at the baseline and 6-months, assessments. \$20 remuneration will be in the form of a Northwestern PNC stored-value card (Visa Gift-Card).

Home Visitors: Home visitors will be asked to respond to a REDCap survey items after completing each MB session to assess if clients came to the session having completed their personal project, implemented session, and next scheduled session date. Home visitors will measure clients' perceived utility and comprehension of text messages by asking clients to rate the extent to which each of the 3 text messages received between sessions was a) useful and b) easy to understand. Questions will be on a 4-point Likert Scale and will be asked of clients at the end of each MB session. These data will be inputted into the HealthySMS system.

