There is no cost to participate in any of the research activities. To ensure all participants in MB-TXT and FAB have access to the required technology for study participation, we have budgeted to purchase and provide no-contract cell phones with 6 months of service and text messaging capability for 25% of the study sample. Prior work with home visiting programs shows that between 70-75% of clients use cell phones as their primary contact with home visitors. We have budgeted to provide cell phones for the 54 participants who will participate in the text message intervention. We will rely on the discretion of the HV to indicate if the HV client will need assistance with minutes. During the referral process we will ask the HV clients if they have a cell phone to be able to participate in the study. There could be a cost to participating if participants have to pay for text messages. However, most people have unlimited text messaging plans included in their mobile phone service. If they incur additional costs, participants may choose not to participate. Participants can opt out at any time by sending the word "STOP."

13.0 Provisions to Protect the Privacy Interests of Participants:

All data records will be identified using an ID number and e-mail only and will not contain other personally identifying information. All data will be collected electronically using (REDCap). The PI and project staff will have minimal contact with clients since all recruitment is being done through the service providers and data collection is being done electronically through a web-based survey. Only authorized persons will be granted access to study data. Passwords and system ID's for the REDCap system will not be shared with other team members. Identifying information (e.g. personal and/or contact information) will be kept separate from the other data. All subject information collected will be kept in secure, password protected files on Northwestern University servers with access restricted to authorized personnel only. Redcap data will be periodically exported to a SPSS database (Statistical Package for Social Sciences) that will only be accessible to study personnel on a password-protected shared project drive.

14.0 Confidentiality and Data Management:

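### Home visitors choose the 1-2 clients they refer in each recruitment window knowing which condition is running, so the arms can differ by selection before baseline

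*Combined protocol and SAP*

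**What the plan says.** Section 7.0, Home Visitors: "Each home-visitor will identify 1-4 client that will participate in study activities", and "of these clients 1-2 will receive MB without Text and 1-2 will receive MB with Text". The same paragraph states that "All home-visitors will implement MB without text and MB with text".

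On order, section 7.0 says "Programs will initially implement MB 1-on-1 and will recruit MB participants for six months before crossing over to recruit MB-TXT participants for 6 months". Section 4.0 (Program Implementation, MB-TXT RCT) gives the same order with a different window length: "Both clusters will initially implement MB 1-on-1 and will recruit MB participants for one quarter". Under Study Conditions, section 4.0 also has the home visitor sending the texts herself.

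On the route into the study, section 4.0 (Participant Screening) says "Participants will initially be screened for eligibility criteria by their home visiting program sites". The program then completes a referral form, with the client's permission, and the study is explained to her on the home visiting side. The research team's call, consent and baseline survey come after that.

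Two places read more like a census. Section 7.0 (Recruitment Procedures/Attrition) says that research staff "will share responsibility for calling each woman receiving HV services", and section 8.0 has women who enrol in home visiting during recruitment periods screened by phone.

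Section 3.0 (Study Participants, Phase 1) limits eligibility to 26 weeks of gestation or less and puts about 80% of the programs' women within the criteria. The Aim 2 analysis (sections 4.0 and 14.0) compares individuals by arm, without adjustment for clustering and with no baseline covariate stated.

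**The concern.** A woman's arm is decided by the window in which her visitor refers her. No later individual randomisation restores balance. The documents do not state in words that the visitor knows the running condition, but it follows from the fixed order and from her delivering both conditions.

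Selection biases the comparison only if it works differently in the two windows. A visitor who favours engaged clients throughout affects generalisability, not the contrast. A visitor who favours them more when texts are on offer affects the contrast itself. The protocol's own rationale (sections 1.0 and 2.0) ties weaker homework engagement to a poorer result from MB. Engagement is something a visitor can see, and it underlies H3.

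The main casualty would be Aim 2, which exists to supply an effect size for planning a larger trial. Any selection difference is added to that estimate, so calling the study a pilot does not remove the problem.

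**Working it through.** **1. The plan's own figure.** Section 14.0 claims more than 80% power on the BDI with 46 per arm for d = 0.59 (two-sided) or 0.52 (one-sided) at 5%.
- Analysed n: 54 × 0.85 = 45.9, rounded to 46 per arm.
- Noncentrality is d × √(n/2), and √(46/2) = 4.80.
- Normal approximation: 80.8% for 0.59 two-sided and 80.2% for 0.52 one-sided. Noncentral t on 90 df: 79.9% and 79.7%.
- The figure is reproduced to within rounding.

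**2. How much choice a visitor has.** Section 7.0 gives 108 clients and about 36 visitors.
- 108 / 36 = 3 clients per visitor, and 54 / 36 = 1.5 per condition.
- A visitor with more eligible women in a window than her 1-2 places must choose among them. Caseload per visitor is not given, so how often this happens is unknown.

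**3. How far clients can be deferred.** A woman at g weeks, with w weeks left before the text window opens, is still eligible when it opens only if g + w ≤ 26.
- Six-month windows (about 26 weeks, section 7.0): for a woman already pregnant when the MB window opens, w = 26, so she cannot be carried over.
- One-quarter windows (13 weeks, section 4.0): she must be at 13 weeks or less when the MB window opens.
- Women who come to notice later in the MB window can be deferred if they are early enough to satisfy the inequality.
- Deferral is therefore restricted but not closed off. Choice within a window is not restricted at all. The Home Visiting Programs paragraph of section 3.0 says only that Phase 1 women be pregnant; on that reading the restriction would be looser.

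**4. What a shift would do (illustration).** Assume no true effect, 46 per arm, and a selection shift b in 6-month BDI, in SD units. The documents give no value for b. The rejection probability comes from the noncentral t with noncentrality b × 4.80 on 90 df.

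| Assumed b | Two-sided rejection (nominal 5%) | One-sided, if b favours MB-TXT | b / 0.59 |
|---|---|---|---|
| 0.1 | 7.6% | 12.1% | 17% |
| 0.2 | 15.8% | 24.4% | 34% |

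The expected Aim 2 effect size is the true effect plus b.

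**5. Would a baseline check or adjustment be enough?**
- With 54 per arm, a two-sided 5% test detects a 0.2 SD baseline imbalance 18% of the time. A non-significant baseline table would not rule selection out.
- If b is the same at baseline and follow-up, adjusting for baseline BDI leaves (1 − ρ) × b. With an assumed ρ of 0.5, a shift of 0.20 SD leaves 0.10 SD. The plan states no such adjustment.

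**The case against.** **The text may describe a census.** Staff call each woman (section 7.0), enrolling women are screened by phone (section 8.0), and 1-4 clients may be an expected yield rather than a licence to pick. This is a fair reading of those sentences alone. But the calls in section 7.0 follow referral forms that the programs complete for women who are eligible and already interested, and a census does not sit with 1-2 clients per condition per visitor. The ambiguity is real; it is not a safeguard. The expected opt-out below 5% concerns women who decline, not women never put forward.

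**Holding clients back.** A reader might infer that visitors can freely save engaged clients for the text window. The 26-week limit does not allow that in general (step 3). What remains is choice within a window and deferral of women early enough to stay eligible.

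**Cell phones.** A reader might infer that phone ownership screens women differently by arm, because section 12.0 says "During the referral process we will ask the HV clients if they have a cell phone to be able to participate in the study". The documents do not support this. The question is put to clients without distinction by arm, and phones are budgeted for text participants, so lacking one need not exclude them.

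**Size.** The illustrative shifts are assumed, and both are below one standard error of the planned contrast, √(2/46) = 0.21 SD. Aim 2 is already described as limited by the pilot design. This stands as a caution about magnitude. It does not make the bias harmless, because bias, unlike sampling error, is not reflected in the confidence interval.

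**Measured correlates.** Behavioral activation, social support, mood regulation, demographics and service use are in the Phase 1 measures, so some correlates of engagement can be compared by arm. That helps, within the limits of step 5.

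**Conclusion.** The concern holds as a risk. Referral is discretionary, the arm is known when it happens, and nothing in the plan constrains or records it. The documents do not show that the arms do differ, or in which direction.

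The size cannot be derived from the documents. The rise in two-sided error from 5% to about 8-16% rests wholly on an assumed outcome shift of 0.1-0.2 SD with 46 per arm and no true effect. A reader might also multiply an assumed trait difference of 0.2-0.4 SD by an assumed correlation with outcome of 0.3-0.5 to get 0.06-0.20 SD, or 10-34% of 0.59. Neither input is in the documents, so that range is no better founded.

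This is a low-cost improvement worth making, because it protects the number that Aim 2 is meant to deliver. It does not address the separate confounding of condition with calendar time that comes from every program starting with MB.

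**What to change.** In section 7.0 (Home Visitors), replace free identification with one rule, used identically in both windows. Each home visitor offers the study to every client meeting the section 3.0 Phase 1 criteria, in the order in which clients become eligible within that window. She refers those who give permission, until her 1-2 for that condition are reached. Clients already eligible on the opening day need a tie-break set in advance and the same in both windows.

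This keeps the permission step of section 4.0, which sending the research team the names of all eligible women would not. It also keeps the per-visitor structure behind the ICC objective in section 4.0 (3 observations in each of 36 visitors), which a program-level quota would disturb.

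In addition:
- Keep a de-identified log, by window, of women eligible, offered the study, referred and enrolled.
- Report baseline characteristics by arm, reading the size of differences rather than p-values.
- Reconcile the Home Visitors paragraph with the census-like wording in sections 7.0 and 8.0, and the one-quarter with the six-month recruitment window.

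The cost is recruitment wording and slightly more list-keeping at the programs. If Phase 1 enrolment is already complete, reconstruct the referral counts as far as possible, report baseline by arm, and state the limitation beside the Aim 2 estimate.
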